#### **4.3.8 Dose Modifications**

The dose of belatacept to be infused is based on the baseline (Day 1) body weight, and will not be modified unless a change in body weight of  $\geq 10\%$  of the Day 1 weight has occurred. If an adjustment has been made based upon a body weight change, this weight should be considered as a new baseline weight. No further adjustment of dose based upon body weight is required thereafter, unless the subject experiences an additional body weight change  $\geq 10\%$  from the new baseline weight. If this occurs, the dose should again be modified, starting with the next belatacept infusion, and that new weight should then be considered as the new baseline weight.

Doses of Thymoglobulin, MMF, EVL and TAC may be adjusted as described in [Section 4.3](#).

In the absence of AEs deemed at least possibly related to study drug treatment, subjects will complete their scheduled belatacept infusions as prescribed by the protocol. If the belatacept infusion can not be administered within the visit/infusion window defined in the protocol, the infusion should be skipped and the next infusion administered within the next visit/infusion window. If a belatacept infusion must be skipped, the investigator should contact the medical monitor in advance to discuss the circumstances. In the event of new, serious, and unexpected toxicity potentially related to belatacept, study drug administration should be interrupted, and the medical monitor promptly notified by the investigator. The subject will be considered eligible to receive additional study drug only after discussion with the medical monitor. Under no circumstances should the dose of belatacept be modified other than for weight changes, as described above. Subjects for whom belatacept dosing is discontinued should be placed on alternative immunosuppressive regimen, to be determined at the discretion of the investigator.

In the event that a subject receives plasmapheresis for the treatment of AR, a discussion of risks and benefits between the investigator and the medical monitor should take place to determine the subject's eligibility to remain in the study on assigned therapy.

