## 8.2 Populations for Analyses

- The primary endpoint will be initially assessed on the ITT population in each treatment group. The ITT population will consist of all randomized and transplanted subjects treated with at least one dose of Thymoglobulin and one dose of study treatment, either belatacept or TAC, and will be included in the safety and efficacy analysis data sets. In these analyses, CSBPARs occurring after discontinuation from assigned therapy will be counted in the treatment arm to which the subject was originally randomized.
- Additionally, for CSBPAR, a sensitivity analysis will be performed with right censoring at the time of discontinuation from the assigned therapy.
- An as-treated analysis will be based on the treatment regimen received. Analysis of treatment differences in the rates of CSBPAR will only include those subjects who remain on their original therapy from the beginning, through the designated analysis time point(s) (e.g., the Months 6, 12 and 24 study visits) for these above mentioned analyses. Treatment differences in the rates of CSBPAR will also be performed using a per protocol efficacy dataset.
  - This is defined as the set of all data derived from that subset of subjects once treated, are followed up consistently with all study criteria to the extent that no relevant protocol deviations have been identified.

The primary analysis will be done on the ITT population and the sensitivity analyses on the primary endpoints will be done in the As Treated, as well as the Per Protocol population.

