6.2 Populations for Analyses

- The “Intent-to-Treat” (ITT) population includes all subjects who are randomized, transplanted and treated with at least one dose of thymoglobulin and one dose of study treatment, either belatacept or TAC. Subjects will be grouped according to the treatment to which they are randomized.
- The “As Treated” (AT) population includes all subjects who are randomized, transplanted and treated with at least one dose of thymoglobulin and one dose of study drug, either belatacept or TAC. Subjects will be grouped according to the treatment which they actually received. The “As Treated” treatment group is the same as the “As Randomized” treatment group, except in cases where a subject received a different treatment from the one he/she was randomized to for the entire course of their participation in the study. In this case, the “As Treated” treatment group is set to the treatment the subject actually received. In cases where a subject received different treatments after randomization, then the “As Treated” treatment group is the first treatment received. Safety reporting will be done in the “As Treated” population.
- The “Per-Protocol” (PP) population includes all randomized subjects who do not violate terms of the protocol that might affect key study outcomes. The protocol specific definitions for “relevant” protocol deviations are described in [APPENDIX 2](#).
- The PK population includes subjects who receive at least one dose of belatacept and have at least 1 post baseline sample available for PK analyses.

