7 STATISTICAL ANALYSES

7.1 Modifications to the Analyses Specified in the Protocol

Due to the reduction in sample size resulting from premature termination of enrollment as of 31 December 2016, it has been deemed appropriate to revise selected statistical analyses specified in the study protocol [Section 8](#). The following modifications to and clarifications of the analyses have been made:

- 1) All analyses will be performed for the whole study treatment period (i.e. 24 months), including analyses at 6 or 12 months.

- 2) Treatment differences will be produced only for the endpoints specified in the sections of this SAP itemized below, instead for all study endpoints.
- 3) Analysis of acute rejections:
 - a) The treatment differences in the severity grades and therapeutic modalities will not be calculated.
 - b) The sensitivity analyses using the per-protocol population will be performed if there are at least 10% of subjects with a protocol deviation in either treatment groups.
 - c) The sensitivity analyses using the as-treated population will be performed if there are at least 10% of subjects in either treatment group for whom the as-randomized treatment group is different from the as-treated treatment group.
 - d) The sensitivity analysis using right censoring at the time of discontinuation from assigned therapy will not be produced. Acute rejections occurring more than 56 days after the last dose date will be flagged in the listing.
 - e) The descriptive summaries by treatment group for cGFR, graft and subject survival, donor specified antibodies, infection and malignancy at Month 12 for subjects with and without AR by Month 6, and at Month 24 in subjects with and without AR by Month 12, will not be produced. The information regarding these parameters will be included in listings that correspond to the specific analyses of these endpoints.
- 4) Analysis of subject and graft survival:
 - a) A listing including all subjects who died or lost their graft will be produced. Corresponding summaries, treatment differences and time to event analysis will be produced if there are at least 5 subjects across treatment groups who died or experienced graft loss during the 24 Month treatment period.
 - b) Any summaries mentioned above, if to be produced, will only be produced for the whole 24 Month treatment period. The corresponding analyses at 6 and 12 months will not be produced.

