7.6.1 Primary Endpoints

7.6.1.1 Acute Rejection

Rates of acute rejection will be summarized by treatment group at Months 6, 12 and 24 using point estimates of the proportion of subjects experiencing at least one CSBPAR, and the corresponding 95% CIs. Two-sided 95% CIs will also be generated for the difference between the two treatment regimens. Descriptive statistics will be provided for the percentages of subjects with CSBPAR in each treatment group, including those for severity grade and treatment received (corticosteroids, lymphocyte depleting agents, renal replacement therapy, plasmapheresis, IVIg, rituximab). All grades of acute rejection, excluding those assessed by the pathologist as "borderline changes" (biopsy findings "suspicious" for acute cellular rejection per the Banff criteria), will be included in the analysis of the primary and relevant secondary endpoints for acute rejection. Sensitivity analyses will be performed, including acute rejections assessed by the pathologist as 'borderline changes' (biopsy findings "suspicious" for acute cellular rejection per the Banff criteria).

In addition, Kaplan-Meier (KM) cumulative event rates will also be performed by treatment groups and the corresponding hazard ratio will be calculated using cox proportional hazard model for the whole study treatment period (i.e. 24 months).

A corresponding listing including all suspected acute rejection events, regardless of when they occurred, will be provided. All events occurring more than 56 days since last dose date will be flagged.

An additional listing will be produced including subjects who post-CSBPAR, are reported to have developed infection or malignancy.

Sensitivity analyses

Sensitivity analyses will be performed on the PP population as well as on the AT population for the primary analysis, if there are in either treatment group at least 10% of subjects with a protocol deviation or subjects for which the as-randomized treatment group is different for the as-treated treatment group, respectively. The table below is a summary of the analysis along with the populations it will be performed in.

Table 7.6.1.1-1: Overview of Sensitivity Analysis

Measure of Interest	Analysis Method	Sensitivity Analysis Population
Proportion of subjects who experience a CSBPAR at 6, 12 and 24 months post-transplant	Point estimate of the proportion and 95% CI* within each treatment group at 6 months	AT and PP

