APPENDIX 2 RELEVANT PROTOCOL DEVIATION CRITERIA

Table 9-2: Relevant Protocol Deviation Criteria

Per-Protocol Deviation Code	Per-Protocol Deviation	Type
1.	Recipients with EBV serostatus negative or unknown	Serious Breach
2.	Genetically-identical donor recipient pairs (i.e., identical twins)	Serious Breach
3.	
 • Subjects with previous graft loss due to AR • Subjects with a positive T-cell or B-cell cross match • Recipients of extended criteria deceased donor (ECD) kidney, as defined in the protocol • Subjects receiving paired (dual or en bloc) kidney transplants 
 • CMV-negative subjects scheduled to receive a kidney from a CMV-positive donor • Subjects with a past history of or current need of desensitization therapy 	Subject Violation
4.	
Any of the following conditions apply:
 
 • Subjects with a recent (within 3 months prior to transplant) PRA \geq 20% • Donor age < 10 years Recipient age < 18 or > 75 at screening 	Serious Breach
5.	
Subjects with underlying renal disease of:
 
 • Primary focal segmental glomerulosclerosis 
 • Type I or II membranoproliferative glomerulonephritis 
Atypical hemolytic uremic syndrome (HUS) / thrombotic thrombocytopenic purpura
	Serious Breach
6.	
Any of the following conditions apply:
 
 • Subjects receiving maintenance immunosuppressive agents for other indications, such as 	Subject Violation

Table 9-2: Relevant Protocol Deviation Criteria

Per-Protocol Deviation Code	Per-Protocol Deviation	Type
7.	treatment of autoimmune disease. 
 • Subjects received treatment other than assigned study medication Subjects with Body mass index (BMI) > 35kg/m ² for non-diabetic and >30kg/m ² for diabetic subjects at screening	Serious Breach

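### SAP Appendix 2 code 6 has no time or event limit, so as written a change of therapy after a rejection removes the subject from the per-protocol rejection analyses

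*SAP*

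**What the plan says.** SAP 6.2 defines the PP set at the level of the whole subject: the "population includes all randomized subjects who do not violate terms of the protocol that might affect key study outcomes", with the relevant deviations listed in Appendix 2. Protocol 8.2 is similar, keeping subjects who "are followed up consistently with all study criteria to the extent that no relevant protocol deviations have been identified". Neither definition stops at the event or at the time point being analysed.

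Almost every entry in Appendix 2, Table 9-2 is an eligibility criterion. The exception is "Subjects received treatment other than assigned study medication". The table breaks across a page at this point; I take the entry as the second condition under code 6.

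The PP set serves a sensitivity analysis of acute rejection. SAP Table 7.6.1.1-1 names as its first measure "Proportion of subjects who experience a CSBPAR at 6, 12 and 24 months post-transplant", followed by the difference between arms and the time to CSBPAR. SAP 7.1 item 3b makes the analysis conditional: it "will be performed if there are at least 10% of subjects with a protocol deviation in either treatment groups".

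The primary analysis treats switching differently. Under protocol 8.2, "CSBPARs occurring after discontinuation from assigned therapy will be counted in the treatment arm to which the subject was originally randomized".

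**The concern.** Code 6 depends on treatment received after randomization, so the outcome can trigger it. Protocol 4.3.8 provides for conversion: "Subjects for whom belatacept dosing is discontinued should be placed on alternative immunosuppressive regimen". The same section calls for a discussion of whether a subject given plasmapheresis for rejection should stay on assigned therapy. SAP 8.3 recognises lack of efficacy as a reason for stopping study medication. A subject who rejects and is then converted would leave both numerator and denominator of the analysis that measures rejection. Because exclusion is of the whole subject, a switch at Month 20 would also remove that subject from the Month 6 result.

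The PP set carries some weight here. SAP 7.1 item 3d drops the analysis censored at discontinuation. SAP 6.2 groups the as-treated population by the first treatment received, so later switchers do not move. PP is therefore the one remaining analysis population for CSBPAR that responds to switching. If conversions are coded as deviations, they also count toward the 10% trigger.

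**Working it through.** **Inputs.** n = 35 per arm, with planning CSBPAR rates of 3.8% (belatacept + EVL) and 3% (TAC + MMF), all from SAP 5. Within-arm intervals are Clopper-Pearson, as footnoted in SAP Table 7.6.1.1-1. The documents give no number of switches, so the counts below are assumptions.

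**The plan's own figures.** Clopper-Pearson with x = 35p gives 0.21% to 16.37% for 3.8% and 0.09% to 15.14% for 3%. These match the stated 0.2% to 16.4% and 0.1% to 15.1%. The plan gives no figure for the PP analysis.

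**Effect of the rule.** Let x be the rejectors in an arm, s the rejectors removed for switching, and m the non-rejectors removed for switching.

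- ITT rate = x/35.
- PP rate = (x − s)/(35 − s − m).
- With m = 0 and s ≥ 1, PP is below ITT when 35(x − s) < x(35 − s), that is, when x < 35. Removing rejectors alone therefore always lowers the rate.
- Setting PP equal to ITT gives the break-even m = s(35 − x)/x. For x = 5 this is m = 6s: 6 removals for s = 1 and 12 for s = 2.
- If every rejector is removed (s = x) and anyone is left in the arm, PP is 0% whatever m is.

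| x | s | m | ITT (95% CI) | PP (95% CI where computed) |
|---|---|---|---|---|
| 1 | 1 | 0 | 1/35 = 2.9% (0.1 to 14.9) | 0/34 = 0% (0 to 10.3) |
| 3 | 1 | 0 | 3/35 = 8.6% (1.8 to 23.1) | 2/34 = 5.9% (0.7 to 19.7) |
| 5 | 4 | 0 | 5/35 = 14.3% (4.8 to 30.3) | 1/31 = 3.2% (0.1 to 16.7) |
| 5 | 2 | 12 | 5/35 = 14.3% | 3/21 = 14.3% |
| 5 | 2 | 13 | 5/35 = 14.3% | 3/20 = 15.0% |
| 5 | 0 | 5 | 5/35 = 14.3% | 5/30 = 16.7% |

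At the planning rates about one event per arm is expected (35 × 3.8% = 1.33; 35 × 3% = 1.05), so the first row is the case closest to the plan's assumptions.

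**Trigger.** 10% of 35 is 3.5, so 4 subjects in either arm. One switched rejector (1/35 = 2.9%) does not trigger the analysis alone. It would take three more deviations in that arm, or four in the other. If the three were non-rejecting switchers in the same arm, the trigger would be met (4/35 = 11.4%) and the PP rate would be 0/31 = 0%. The third row meets the trigger by itself.

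**Is the entry limited elsewhere?** I find no limit in SAP 6.2, 7.1, 7.6.1.1 or Appendix 2. Where a limit was wanted, it was written. The SAP as-treated definition reassigns a subject only if the other treatment was received throughout participation. The as-treated analysis in protocol 8.2 looks at therapy only up to the time point analysed. Code 6 has neither limit.

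**The case against.** The strongest reply is that code 6 was never meant to cover conversions. The PP set excludes those who violate the protocol, and a conversion the protocol provides for is not a violation. The entry sits among eligibility criteria and may mean only that the wrong treatment was given. That reading is reasonable and would be harmless, but the text does not state it, and a programmer following the text could code any change of therapy.

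Three stronger inferences are tempting, and the documents do not support them:

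- *The PP rate is biased low.* This holds for the removal of rejectors alone. Switchers who never rejected also leave, which raises the rate, and their number is unknown.
- *Rejectors will generally be switched, mostly in one arm.* The conversions in protocol 4.3.3 to 4.3.5 are for intolerance. Rejection is not among the mandatory reasons to discontinue in protocol 3.5, and the rejection guidelines in 5.3.10 do not call for a switch. The link rests on the plasmapheresis discussion and alternative regimen in 4.3.8, and on lack of efficacy in SAP 8.3, which appears there only in a rule for missing survival status. No arm is singled out.
- *Anti-rejection medication itself triggers code 6.* Protocol 5.3.10 provides for that treatment, so it is probably not meant to be covered.

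It also stands that the consequence is limited. The study is descriptive with no tests, and subjects with relevant deviations and all suspected rejections are listed (SAP 7.3 and 7.6.1.1), so removals can be traced.

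**Conclusion.** The concern holds as a defect in the rule as written: an exclusion with no date or event limit allows the outcome to decide who is in the set that measures it. It rests on a literal reading of code 6 and on at least one subject changing therapy after a rejection. With events this sparse, one such removal can take an arm to 0%, but the net effect on the PP rate cannot be signed or sized from the documents. The damage is confined to a sensitivity analysis that may not run. It should be corrected before database lock because the analysis, if run, would be read as a check on the primary result.

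**What to change.** In SAP Appendix 2, reword the code 6 entry to: *Subject's initial maintenance treatment was not the assigned treatment.* Add: *No subject is excluded from the PP set because of treatment given on or after the onset of the first CSBPAR, or after the analysis time point concerned.*

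Subjects who switch before any rejection then stay in the PP set with all their follow-up and events, as in the ITT analysis. It would be a mistake to cut their follow-up at the date of change. SAP 8.3 counts a rejection-free subject with incomplete follow-up as having no rejection, so they would enter the proportions as non-events while later rejections were discarded. It would also bring back the censoring that SAP 7.1 item 3d removed.

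The cost is two sentences and one programming condition before lock, with no new data. If the narrow meaning was intended all along, the change only states it.

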APPENDIX 3 LIST OF PERI-INFUSIONAL EVENTS

List of peri-infusional events (infusion related reactions) is obtained from the preferred terms that correspond to the BMS predefined list of MedDRA preferred terms (Infusion -related reactions-EU- SMQ_CODE BMS03061). The peri-infusional events are those occurring within 24 hours of Belatacept administration. The latest MedDRA Version of the list of events at the time of the database lock will be used.

APPENDIX 4 MARKED LABORATORY ABNORMALITY CRITERIA

Thresholds for defining markedly abnormal laboratory analyte values (per National Cancer Institute Common Terminology Criteria for Adverse Events (NCI CTCAE), version 4.0 (published 29-May-2009)).

Analyte	Formatted Value	Code	Lower threshold for Marked Abnormality			Upper threshold for Marked Abnormality		
			US conventional unit	Conventional units	SI Units	US conventional unit	Conventional units	SI Units
Hemoglobin	Hemoglobin	HB	< 8.0g/dL	< 8.0g/dL	< 80g/L	More than 4.0g/dL > ULN*	More than 4.0g/dL > ULN*	More than 40g/L > ULN
White blood cell (WBC) count	Leukocytes	WBC	< 2.0 x 10 [*] 9C/L (10 * 9 C/L = 10 * 3C/uL)	< 2,000/mm ³	< 2.0 x 10 [*] 9C/L			
Absolute lymphocytes	Lymphocytes (absolute)	LYMPA	< 0.5 x 10 [*] 9C/L (10 * 9C/L = 10 * 3C/uL)	< 500/mm ³	< 0.5 x 10 [*] 9C/L	> 20 x 10 [*] 9C/L	> 20,000/mm ³	> 20 x 10 [*] 9C/L
Absolute neutrophils	Neutrophils (absolute)	NEUTA	< 1.0 x 10 [*] 9C/L (10 * 9C/L = 10 * 3C/uL)	< 1,000/mm ³	< 1.0 x 10 [*] 9C/L			
Platelets	Platelet Count	PLAT	< 50 x 10 [*] 9C/L (10 * 9C/L = 10 * 3C/uL)	< 50,000/mm ³	< 50 x 10 [*] 9C/L			
Serum creatinine	Creatinine	CREAT				> 3.0mg/dL	> 3.0mg/dL	> 265umol/L
Urinary protein/creatinine ratio	Protein/Creatinine Ratio	PRCRR				≥ 3500mg/mg creatinine	≥ 3.5g/mg creatinine	> 395mg/mmol creatinine
Serum sodium [Na]	Sodium, Serum	NA	< 130mEq/L	< 130mEq/L	< 130mmol/L	> 155mEq/L	> 155mEq/L	> 155mmol/L

Analyte	Formatted Value	Code	Lower threshold for Marked Abnormality			Upper threshold for Marked Abnormality		
Serum potassium [K]	Potassium, Serum	K	< 3.0mEq/L	< 3.0mEq/L	< 3.0mmol/L	> 6.0mEq/L	> 6.0mEq/L	> 6.0mmol/L
Bicarbonate [HCO ₃]	Bicarbonate	HCO3	< 11mEq/L	< 11mmol/L	< 11mmol/L			
Serum calcium [Ca]	Calcium, Total	CA	< 7.0mg/dL	< 7.0mg/dL	< 1.75mmol/L	> 12.5mg/dL	> 12.5mg/dL	> 3.1mmol/L
Serum magnesium [Mg]	Magnesium, Serum	MG	< 0.8mEq/L	< 0.9mg/dL	< 0.4mmol/L	> 2.5mEq/L	> 3.0mg/dL	> 1.23mmol/L
Serum phosphorus [P]	Phosphorus, Inorganic	PHOS	< 2.0mg/dL	< 2.0mg/dL	< 0.6mmol/L			
Serum albumin	Albumin	ALB	< 2.0g/dL	< 2.0g/dL	< 20g/L			
Serum uric acid	Uric Acid	URIC				> 10.0mg/dL	> 10.0mg/dL	> 0.59mmol/L
Fasting blood glucose	Glucose, Fasting Serum	GLUCF	< 40mg/dL	< 40mg/dL	< 2.2mmol/L	> 250mg/dL	> 250mg/dL	≥ 14.0mmol/L
Cholesterol	Cholesterol, Total (TC)	CHOL				> 400mg/dL	> 400mg/dL	> 10.3mmol/L
Triglycerides	Triglycerides, Fasting	TRIGF				> 500mg/dL	> 500mg/dL	> 5.7mmol/L
Serum aspartate aminotransferase (AST)	Aspartate Aminotransferase (AST)	AST				> 5.0 x ULN*	> 5.0 x ULN	> 5.0 x ULN
Serum alanine aminotransferase (ALT)	Alanine Aminotransferase (ALT)	ALT				> 5.0 x ULN*	> 5.0 x ULN	> 5.0 x ULN
Serum alkaline phosphatase	Alkaline Phosphatase (ALP)	ALP				> 5.0 x ULN*	> 5.0 x ULN	> 5.0 x ULN
Serum total bilirubin	Bilirubin, Total	TBILI				> 3.0 x ULN*	> 3.0 x ULN	> 3.0 x ULN

* ULN: Upper limit of laboratory reference range. Note: ULN should be in the same unit.

** Threshold not defined in NCI CTCAE v. 4.0

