4.2 Secondary Endpoint

The two treatment groups will be compared for all secondary endpoints.

Acute Rejection

- Treatment differences in the incidence of CSBPAR at 6, 12 and 24 months post transplant, in the belatacept + EVL versus TAC + MMF treatment groups.
- Time to CSBPAR.
- Treatment differences in the severity grades and therapeutic modalities used to treat all episodes of CSBPAR at 6, 12, and 24 months post-transplant:
 - Severity: To be assessed by each local pathologist using the 2007 update to the Banff 97 classification of renal allograft pathology).

- Treatment regimen: Categorical analysis of CSBP/AR episodes by treatment received, including: a) corticosteroids; b) lymphocyte depleting therapy; c) renal replacement therapy; d) plasmapheresis; e) IVIg; f) rituximab.

Subject and Graft Survival

- Proportion of all subjects who survive with a functioning graft at 6, 12 and 24 months post-transplant.
- Proportion of all subjects who experience death by 6, 12 and 24 months post-transplant.
- Proportion of all subjects who experience graft loss by 6, 12 and 24 months post-transplant.
- Time to event analysis of death or graft loss.

Renal Function

- Absolute (mean and median) cGFR values at 3, 6, 12 and 24 months post-transplant, as determined from the 4-variable Modification of Diet in Renal Disease (MDRD) formula.
- The mean changes from Month 3 cGFR at 6, 12, and 24 months post-transplant.
- Slope of the change in cGFR from Month 3 to Months 6, 12 and 24 post-transplant.
- The mean urine protein to creatinine ratio ($U_{Pr/Cr}$) at 3, 6, 12 and 24 months post-transplant.

Donor Specific Anti-HLA Antibodies (DSA)

- The percentage of subjects with, and titers of pre-existing (pre-transplant) and *de novo* (post-transplant) anti-HLA DSA on Day 1 (pre-transplant, pre-dose), and at Months 12 and 24, respectively.
- Characterization of any *de novo* DSA detected by IgM and IgG classes, and by the presence or absence of complement fixing properties.

Safety and Tolerability of each Treatment Regimen

- Incidence of all AEs and SAEs at 6, 12, and 24 months post-transplantation.
- Incidence of ESI at 6 months, 12 months, and 24 months
- Description and incidence of clinically significant changes in vital signs.
- Description and incidence of laboratory test marked abnormalities.

Cardiovascular and Metabolic Co-Morbidities

- Incidence of New Onset Diabetes After Transplantation (NODAT) at 6, 12, and 24 months post-transplant.

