6 STUDY PERIODS, TREATMENT REGIMENS AND POPULATIONS FOR ANALYSES

6.1 Treatment Regimens

Approximately 70 subjects (n=35 per arm) receiving de novo kidney transplants will be randomized (stratified by study site/center) in a 1:1 ratio to 1 of the following 2 treatment groups:

- Thymoglobulin + Belatacept + Everolimus.
- Thymoglobulin + Tacrolimus + MMF.

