7.7.2 Laboratory Test Analysis

Laboratory marked abnormalities as identified using pre-defined criteria (see [APPENDIX 4](#)), will be descriptively summarized with frequency and percentage. All laboratory values of a laboratory analyte will be listed for subjects with at least one marked abnormality for this parameter will be listed (independent of study period).

All available laboratory parameters included in the Hematology and Chemistry Panels in protocol Section 5.3.6.1 will also be summarized over time (with mean, SD, median, minimum, Q25, Q75, and maximum).

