8.7 Safety Data Conventions

Safety data will be handled according to the BMS safety data convention standards and Supplement to Safety Guidelines for BMS-224818.

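### SAP Appendix 4: the two conventional-unit limits for the urine protein/creatinine ratio are about 1,000 times the SI limit in the same row

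*SAP*

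**What the plan says.** The urinary protein/creatinine ratio row of SAP Appendix 4 has one upper limit in three columns:

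- US conventional: "≥ 3500mg/mg creatinine"
- Conventional: "≥ 3.5g/mg creatinine"
- SI: "> 395mg/mmol creatinine"

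SAP 7.7.2 puts the table to two uses. "Laboratory marked abnormalities as identified using pre-defined criteria" are summarised by frequency and percentage, with Appendix 4 cited as the source of the criteria. The table also selects subjects for the listing: "All laboratory values of a laboratory analyte will be listed for subjects with at least one marked abnormality for this parameter". The summary serves a secondary safety endpoint in SAP 4.2: "Description and incidence of laboratory test marked abnormalities".

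The visible SAP text does not say which unit column is applied. SAP 8.7 refers safety data handling to the "BMS safety data convention standards and Supplement to Safety Guidelines for BMS-224818", which are not part of the documents, and part of SAP Section 8 is redacted. Either may settle the column.

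**The concern.** The three entries should be the same limit written three ways, as in the rest of the table. The two conventional entries agree with each other, since 3.5 g is 3500 mg and both are per mg of creatinine. A ratio of 3500 mg of protein per mg of creatinine is, however, far from 395 mg per mmol.

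At stake is whether the flag can fire. If a conventional limit is programmed with its printed unit, a subject with heavy proteinuria is neither counted nor listed, and the table shows a 0% row that reads as a safety result. Severity of proteinuria is a secondary objective (SAP 3.2), and the visible SAP contains no other threshold count for this ratio.

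**Working it through.** **Inputs, all from SAP Appendix 4 unless noted**

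- Ratio limits: 3500 mg/mg, 3.5 g/mg, 395 mg/mmol.
- Serum creatinine limit, used as the conversion pair: 3.0 mg/dL and 265 umol/L.
- Planned arm size: 35 (SAP 6.1).

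**Step 1. Mass of creatinine per mmol**

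3.0 mg/dL = 30 mg/L and 265 umol/L = 0.265 mmol/L, so 30 / 0.265 = 113.2 mg/mmol.

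**Step 2. SI limit as a mass ratio**

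395 / 113.2 = 3.489 mg/mg, which is 3,489 mg/g.

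**Step 3. Compare with the conventional entries**

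- 3500 / 3.489 = 1,003. The entry of 3.5 g/mg is the same quantity, so it has the same ratio.
- In the other direction, 3500 × 113.2 is about 396,000 mg/mmol against the printed 395.
- Allowing for rounding of 265 (264.5 to 265.5) and of 395 (394.5 to 395.5), the ratio stays between 1,000 and 1,006.

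**Step 4. Try g for mg in the denominator**

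3500 mg/g = 3.5 g/g = 3.5 mg/mg, and 3.5 × 113.2 = 396.2 mg/mmol. This is 0.3% above 395, so this one change reconciles all three entries.

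**Step 5. Is this the table's usual rounding?**

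Rows that can be checked with a unit pair printed elsewhere in the documents:

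| Row | Converted | Printed SI value | Gap | Pair used |
|---|---|---|---|---|
| Hemoglobin 8.0 g/dL | 80 g/L | 80 g/L | 0% | decimal |
| Calcium 12.5 mg/dL | 12.5 × 1.75/7.0 = 3.125 mmol/L | 3.1 | 0.8% | calcium lower limit |
| Magnesium lower 0.9 mg/dL | 0.9 × 1.23/3.0 = 0.369 mmol/L | 0.4 | 8.4% | magnesium upper limit |
| Magnesium upper 2.5 mEq/L | 2.5 × 0.4/0.8 = 1.25 mmol/L | 1.23 | 1.6% | magnesium lower limit |
| Glucose 250 mg/dL | 250 × 11.1/200 = 13.9 mmol/L | 14.0 | 0.9% | protocol 5.3.15 |
| Triglycerides 500 mg/dL | 5.65 mmol/L | 5.7 | 0.9% | protocol Table 5.3.16-1 |
| Cholesterol 400 mg/dL | 400 × 2.59/100 = 10.36 mmol/L | 10.3 | 0.6% | LDL pair, protocol Table 5.3.16-1 |

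The largest gap is about 8%; none approaches a factor of 1,000. Phosphorus and uric acid have no second pair in the documents and were not checked.

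**Step 6. Could the printed limit be reached?**

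Assume urine creatinine of 20 to 200 mg/dL (an assumption; the documents give no range). At 3500 mg/mg the urine would need 3500 × 20 = 70,000 mg/dL = 700 g/L of protein at the low end, and 3500 × 200 = 700,000 mg/dL = 7,000 g/L at the high end. At 3.5 mg/mg the requirement is 0.7 to 7 g/L. On that assumption the printed conventional limit cannot be met.

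**Step 7. Effect on the row**

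Per arm, 1/35 = 2.9%, 2/35 = 5.7% and 3/35 = 8.6%. The number of subjects above 3.5 mg/mg is not given. If it is taken as 0 to 3 per arm, the row is understated by 0 to 8.6 percentage points.

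**The case against.** The strongest reply accepts the arithmetic and disputes the consequence.

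- **Reporting unit.** The laboratory's unit is not stated; protocol 5.3.6.1 names the ratio without one. The bare number 3500 applied to results in mg/g flags correctly, and so does 3.5 applied to results in g/g or mg/mg. Failure needs the printed unit to be taken literally, or the number to be paired with the wrong unit. This stands, and it is why the consequence is stated conditionally and why the fix includes a programming check.
- **Governing rule.** SAP 7.7 and protocol 8.4.3 define marked abnormalities by the central laboratory manual, while SAP 7.7.2 points to Appendix 4. If the manual governs, the printed entries drive nothing. That conflict affects every analyte and is a separate matter. It limits the impact but does not make the row consistent.
- **Size in percentage points.** The 0 to 3 subjects per arm and the urine creatinine range are assumptions. The safety analysis uses the As Treated population, so the actual denominator may be below 35. Only the factor of about 1,000 is established by the documents.
- **Residual differences.** The conventional entries use ≥ and the SI entry uses >, and 396 is not exactly 395. Both are immaterial beside a 1,000-fold gap.
- **A mere typing slip.** It probably is one, but it sits in a limit that SAP 7.7.2 uses to count and list subjects, so it can change an output. A fault in reading the PDF is unlikely, because two separately written entries, one in mg and one in g, carry the same denominator and agree with each other.

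**Conclusion.** The concern holds. Two of the three limits in this row are about 1,003 times the third (1,000 to 1,006 over rounding), shown from the table's own creatinine figures without an outside constant.

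The effect depends on three things: Appendix 4 being the rule applied, a conventional limit being programmed with its unit as printed, and at least one subject exceeding about 3.5 mg/mg. If nobody does, a 0% row is correct under any column.

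The reach is narrow: one descriptive row and its listing. The primary endpoint and the ratio summaries and model in SAP 7.6.2.3 do not use the limit. It should still be corrected before the table is run, because the error is certain and the correction is nearly free.

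**What to change.** In SAP Appendix 4, change the two conventional entries to 3500 mg/g creatinine and 3.5 g/g creatinine, which agree with the SI entry of 395 mg/mmol to within 0.3%. The ≥ and > signs can be aligned in the same edit.

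Before the marked-abnormality table and listing are produced, confirm that the programmed limit is in the unit in which the central laboratory reports the ratio.

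The cost is two table cells and one programming check. No new data are needed, and no other row or analysis changes.
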